**Name of active substance:**

PBTZ169 Hydrochloride

---

State Budgetary Health-Care Institution of the Arkhangelsk Region Arkhangelsk Clinical Tuberculous Dispensary Address: [name] Principal investigator: [name]

Study Center 9:

Regional State Budgetary Health-Care Institution Tomsk Phthisiatric and Pulmonologic Medical Center Address: [name] Principal investigator: [name]

Study Center 10:

State Health-Care Institution of the Samara Region Tolyatti Municipal Tuberculous Dispensary Address: [name] Principal investigator: [name]

Study Center 11:

Federal State Budgetary Institution Novosibirsk Tuberculosis Research Institute of the Ministry of Health Care of the Russian Federation Address: [name] Principal investigator: [name]

Study Center 12:

State Autonomous Health-Care Institution Republican Clinical Tuberculosis Dispensary Address: [name] Principal investigator: [name]

Study Center 13:

Federal State Budgetary Institution Saint Petersburg Research Institute of Phthisiopulmonology of the Ministry of Health Care of the Russian Federation Address: [name] Principal investigator: [name]

**Publications (references):** none**Phase of drug development:** IIa

**Goals:** to study the efficacy of PBTZ169 in the daily doses of 160, 320, and 640 mg based on its early bactericidal activity, safety, and pharmacokinetics of PBTZ169 p.o. as monotherapy for 14 days in patients with newly diagnosed microbiologically proven respiratory tuberculosis with preserved susceptibility to Isoniazid and Rifampicin.

**Design:** this study is a randomized open-label study of efficacy (in terms of early bactericidal activity), safety, and pharmacokinetics of PBTZ169 in parallel groups with active control in patients with newly diagnosed respiratory tuberculosis. The study comprises the following stages:

**Name of active substance:**PBTZ169 Hydrochloride

---

---

- Screening, up to 10 days
- Monotherapy, 14 days
- Follow-up, 7 days

Screening procedures are carried out within 10 days before randomization. Screening procedures can be carried out on an outpatient or inpatient basis. If the screening procedures are performed outpatiently, subjects are admitted to hospital on the day before the first dose of the study drugs. If the screening procedures are performed inpatiently, subjects stay hospitalized for the purpose of participation in the clinical study.

Eligible subjects are randomized. During randomization, each subject is assigned a randomization number generated by the IWRS. Each patient is assigned to one of the following four groups based on the randomization number:

- Group 1: subjects receive PBTZ169 capsules at a daily dose of 160 mg for 14 days as a monotherapy, after which the drug is discontinued, and standard antituberculosis therapy is prescribed (hereinafter, standard antituberculosis therapy is defined as the tuberculosis therapy provided for under Order of the Ministry of Health of the Russian Federation No. 951 dated December 29, 2014). Up to 15 subjects are planned to be randomized to this group.
- Group 2: subjects receive PBTZ169 capsules at a daily dose of 320 mg for 14 days as a monotherapy, after which the drug is discontinued, and standard antituberculosis therapy is prescribed. Up to 15 subjects are planned to be randomized to this group.
- Group 3: subjects receive PBTZ169 capsules at a daily dose of 640 mg for 14 days as a monotherapy, after which the drug is discontinued, and standard antituberculosis therapy is prescribed. Up to 15 subjects are planned to be randomized to this group.
- Group 4: subjects receive isoniazid tablets at a standard daily dose of 600 mg for 4 days as a monotherapy, after which standard antituberculosis therapy follows. Up to 7 subjects are planned to be randomized to this group.

All study procedures are conducted in the subjects and documented under the randomization number.

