**Name of active substance:**

PBTZ169 Hydrochloride

---

Nocturnal sputum is collected from all subjects in the morning at V1. After that, every patient received the study drug (PBTZ169 or isoniazid) as a monotherapy for 14 consecutive days. After 14 days of monotherapy (Day 15 of the study, V8), PBTZ169 is discontinued in Groups 1 to 3 (Day 14 being the day of the last PBTZ169 dose). Standard therapy is initiated 3 days after the monotherapy end date (Day 18 of the study, V10). Standard therapy drugs are resumed in Group 4 (standard dose of isoniazid) without a break—that is, the day following the monotherapy end date (Day 15 of the study). Patient monitoring during clinical study is continued on a hospital basis and ended 7 days following the monotherapy end date.

Venous blood samples are taken from all subjects in Groups 1, 2, and 3 (PBTZ169 monotherapy) to measure PBTZ169 levels. Blood samples are drawn before the first dose of PBTZ169 (0 min time point) and later at the following time points after the first dose: in 0:20, 0:40, 1:00, 1:30, 2:00, 2:30, 3:00, 4:00, 6:00, 8:00, 10:00, 12:00, and 24:00 (hr:min). Blood samples are also taken before the last dose of PBTZ169 (0 min time point) and later at the following time points after the last dose: after 0:20, 0:40, 1:00, 1:30, 2:00, 2:30, 3:00, 4:00, 6:00, 8:00, 10:00, 12:00, 24:00, 48:00, and 72:00 (hr:min).

All venous blood samples are kept in case any additional parameters have to be measured.

Subjects are hospitalized throughout the monotherapy and follow-up periods.

**Number of subjects:** It's planned to randomize 52 eligible subjects for the study, namely 15 subjects in each PBTZ169 group and 7 subjects in the isoniazid group.

The data of subjects who will receive at least one dose of the study drug and whose study drug concentrations are known will be processed in the final statistical analysis of efficacy and pharmacokinetics.

The data of subjects of ITT population will be processed in the final statistical analysis of safety.

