**Comparator treatment duration:**

Monotherapy for 14 consecutive days. Isoniazid is then continued as part of the combined antituberculosis therapy.

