**Assessment parameters:****Efficacy:*****Primary efficacy endpoint:***

- Early bactericidal activity 14 days from the monotherapy start date (EBA0-14).

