***Efficacy analysis***

According to the EMA Guidance, early bactericidal activity (EBA) assessment should be based on determining the count of live mycobacteria in the patient's sputum during monotherapy with the drug. The primary method of determining mycobacterial count used is inoculating agar with sputum to count CFU/mL. The method is chosen as it is used as the primary method in nearly all studies assessing early bactericidal activity, which means it can be considered conventional [16–19].

The method of quantitative PCR for counting mycobacterial cells in sputum is used as a secondary method for secondary analysis [23].

All assessments of  $\log_{10}$  CFU/mL sputum, mycobacterial cell count estimates obtained with PCR, and their changes from baseline are tabulated by measurement points and treatment groups.

In the primary analysis of treatment efficacy, changes from baseline in  $\log_{10}$  CFU/mL sputum (for agar inoculation) 14 days after the therapy start date are estimated. Changes in  $\log_{10}$  CFU/mL sputum 2 and 7 days after the therapy start date are also estimated in the secondary analysis of treatment efficacy. Early bactericidal activity (EBA) is assessed as a change in  $\log_{10}$  of CFU/mL of sputum specified for the treatment day [24] with a two-sided 95% confidence interval.

Though sample size is estimated empirically disregarding formal comparisons between the two dose levels, the Kruskal–Wallis test is used to compare the values for different dose levels of the study drug at a two-sided 5% significance level.

The history of mean changes in  $\log_{10}$  CFU/mL from baseline by assessment points is presented graphically by treatment groups.

The Jonckheere–Terpstra test is used to identify the trend for the primary efficacy endpoint depending on the increase in dose level (increasing  $EBA_{0-14}$  for increasing doses).

A similar efficacy analysis (based on changes in  $\log_{10}$  cells/mL) is carried out by determining mycobacterial cell count with quantitative PCR.

Graphical methods and calculation of correlation coefficients between individual measurements obtained using the two quantification methods are used to analyze the

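### The Group 4 definition gives 4 days of isoniazid monotherapy; the rest of the synopsis requires 14

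*Combined protocol and SAP*

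**What the plan says.** The groups are defined in the synopsis under Design. Groups 1 to 3 each receive PBTZ169 alone for 14 days. For Group 4 the text reads: "subjects receive isoniazid tablets at a standard daily dose of 600 mg for 4 days as a monotherapy, after which standard antituberculosis therapy follows".

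Four other places bear on the length of isoniazid monotherapy:

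- The list of stages under Design has one entry for the treatment period, "Monotherapy, 14 days", with no exception for Group 4. A 7-day follow-up comes after it.
- The description of the treatment period, also under Design, states that "every patient received the study drug (PBTZ169 or isoniazid) as a monotherapy for 14 consecutive days". It then moves Group 4 to standard therapy with no gap, on Day 15.
- The same description says: "Patient monitoring during clinical study is continued on a hospital basis and ended 7 days following the monotherapy end date".
- Comparator treatment duration reads: "Monotherapy for 14 consecutive days. Isoniazid is then continued as part of the combined antituberculosis therapy".

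The primary efficacy endpoint is "Early bactericidal activity 14 days from the monotherapy start date". The Efficacy analysis section ties EBA to the count of live mycobacteria in "sputum during monotherapy with the drug".

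**The concern.** The statements about Group 4 cannot all be true. If isoniazid is given alone for 4 days and standard therapy follows without a gap, companion drugs start on Day 5, not Day 15.

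The wrong number sits where a reader looks first for an arm's regimen, and a site could carry it out as written. Isoniazid alone is the trial's active control. If companion drugs were added from Day 5, the control arm's fall in log10 CFU by Day 7 and Day 14 would reflect a combination regimen. It would no longer show what isoniazid alone does at the primary time point, and setting the PBTZ169 results beside it would mislead.

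**Working it through.** No sample-size or power figure depends on this number. The sample size is described as empirical, and the planned total checks as 3 × 15 + 7 = 52. The check is therefore a day count.

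**Inputs**

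- First dose on Day 1. This follows from the Design text, which places the last of 14 daily PBTZ169 doses on Day 14.
- Standard therapy in Group 4 starts on Day 15 without a gap (Design).
- Monitoring ends 7 days after monotherapy ends (Design).
- EBA windows of 0-14 days (primary) and 0-7 and 0-2 days (secondary), from Assessment parameters.
- Group sizes of 15, 15, 15 and up to 7 (Design and Number of subjects).

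**Step 1: which duration does the schedule imply?**

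Duration = start of standard therapy − day of first dose = 15 − 1 = 14 days. The stated 4 days is not reproduced; it would require a start on Day 1 + 4 = Day 5.

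**Step 2: does the end of monitoring agree?**

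End of monitoring = last monotherapy day + 7.

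- With 14 days: 14 + 7 = Day 21, which matches the 14-day and 7-day stages.
- With 4 days: 4 + 7 = Day 11, before the Day 14 primary assessment.

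Only 14 days is compatible with measuring the primary endpoint in Group 4.

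**Step 3: what would the 4-day text do to the control arm's EBA?**

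Share of the window on combination therapy = max(0, window − monotherapy days) / window.

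| Window | 4 days of monotherapy | 14 days of monotherapy |
|---|---|---|
| EBA0-14 | (14 − 4)/14 = 10/14 = 71% | 0/14 = 0% |
| EBA0-7 | (7 − 4)/7 = 3/7 = 43% | 0/7 = 0% |
| EBA0-2 | 0/2 = 0% | 0/2 = 0% |

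**Step 4: how many patients are concerned?**

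Up to 7/52 = 13%. The other 45/52 = 87% are in the PBTZ169 groups, whose regimen is stated consistently.

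**Step 5: which planned analyses use the number?**

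Under Efficacy analysis, the Kruskal–Wallis test compares dose levels and the Jonckheere–Terpstra test looks for a trend with increasing dose. Isoniazid has a single dose level, so both tests concern PBTZ169 only. No test against isoniazid is specified. What remains is the tabulated and plotted Group 4 result.

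**The case against.** The strongest reply is that the synopsis largely corrects itself. Two places specific to the comparator say 14 days, one of them a section devoted to its duration, and nothing supports or explains 4. Anyone who reads the whole synopsis will arrive at 14. On that reading every percentage in the table is zero, so the figures describe a course that no text shows anyone took. The sentence saying that every patient received 14 days is in the past tense, which leans towards 14 days having been given. The trial has already stopped, so an edit cannot change treatment.

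Much of this stands. The intended duration is not in doubt, the percentages are conditional, and no planned test changes. It does not make the arm definition correct, though. The surrounding text mixes tenses, so one past-tense verb is weak evidence of what sites did, and the documents contain no dosing data.

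Two further points are fair:

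- Under Number of subjects, the efficacy analysis is limited to dosed patients with known drug concentrations, while blood samples for concentrations are planned only in Groups 1 to 3. Read literally, Group 4 might not enter that analysis at all. That is a separate ambiguity. It sits awkwardly with tabulating efficacy by treatment group, and it does not make 4 days right.
- A digit could have been lost when the PDF was read. Nothing suggests so: the sentence is intact and the three parallel entries kept their 14. A look at the source document would settle it.

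**Conclusion.** The inconsistency is real, and 14 days is the intended duration. The 4-day figure conflicts with the stage list, the treatment-period description, the Day 15 switch, the comparator-duration section and the follow-up arithmetic.

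The consequence is limited. Only if the 4-day text was followed would the control arm lose its meaning as isoniazid alone at Day 14 (71% of the window on combination therapy) and Day 7 (43%). At most 7 patients are involved. Their EBA0-2, all PBTZ169 estimates and both dose-level tests are unaffected. It should be corrected because it is a wrong treatment duration in the definition of a randomised arm, but it does not threaten the trial's main estimates.

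This rests on two assumptions: that Day 1 is the day of the first dose in Group 4 as it is in the PBTZ169 groups, and that the 4 stands in the source document.

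**What to change.** In the Group 4 entry of the group list under Design, change the duration of isoniazid monotherapy from 4 to 14 days. No other text on duration needs to change.

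The section on pharmacokinetic and pharmacodynamic analysis records that the study was terminated early. Before Group 4 results are reported, the sponsor should therefore also confirm from the dosing records how many days each patient took isoniazid alone, and flag as off-monotherapy any sputum count taken after companion drugs began.

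The cost is one number in the text and a record check for at most 7 patients. No extra patients or procedures are needed, and the sample size and significance level stay as they are.

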**Name of active substance:**

PBTZ169 Hydrochloride

---

Nocturnal sputum is collected from all subjects in the morning at V1. After that, every patient received the study drug (PBTZ169 or isoniazid) as a monotherapy for 14 consecutive days. After 14 days of monotherapy (Day 15 of the study, V8), PBTZ169 is discontinued in Groups 1 to 3 (Day 14 being the day of the last PBTZ169 dose). Standard therapy is initiated 3 days after the monotherapy end date (Day 18 of the study, V10). Standard therapy drugs are resumed in Group 4 (standard dose of isoniazid) without a break—that is, the day following the monotherapy end date (Day 15 of the study). Patient monitoring during clinical study is continued on a hospital basis and ended 7 days following the monotherapy end date.

Venous blood samples are taken from all subjects in Groups 1, 2, and 3 (PBTZ169 monotherapy) to measure PBTZ169 levels. Blood samples are drawn before the first dose of PBTZ169 (0 min time point) and later at the following time points after the first dose: in 0:20, 0:40, 1:00, 1:30, 2:00, 2:30, 3:00, 4:00, 6:00, 8:00, 10:00, 12:00, and 24:00 (hr:min). Blood samples are also taken before the last dose of PBTZ169 (0 min time point) and later at the following time points after the last dose: after 0:20, 0:40, 1:00, 1:30, 2:00, 2:30, 3:00, 4:00, 6:00, 8:00, 10:00, 12:00, 24:00, 48:00, and 72:00 (hr:min).

All venous blood samples are kept in case any additional parameters have to be measured.

Subjects are hospitalized throughout the monotherapy and follow-up periods.

**Number of subjects:** It's planned to randomize 52 eligible subjects for the study, namely 15 subjects in each PBTZ169 group and 7 subjects in the isoniazid group.

The data of subjects who will receive at least one dose of the study drug and whose study drug concentrations are known will be processed in the final statistical analysis of efficacy and pharmacokinetics.

The data of subjects of ITT population will be processed in the final statistical analysis of safety.

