**Study drug, dose, administration, and batch number:**

Study drug code: PBTZ169

Brand name: none

International nonproprietary name: none

Dosage form: 80 mg capsules.

Pharmacotherapeutic group: antituberculosis drug

ATC code: J04A

Dose and administration route: patients receive PBTZ169 orally once a day in the morning in the fasting state in the following doses:

- Group 1: 160 mg daily
- Group 2: 320 mg daily
- Group 3: 640 mg daily

**Name of active substance:**PBTZ169 Hydrochloride

---

---

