**Comparator, dose and administration, batch number:**

Brand name: Isoniazid

International nonproprietary name: isoniazid

Dosage form: 300 mg tablets.

Pharmacotherapeutic group: antituberculosis drug

ATC code: J04AC01

Dose and administration route: Isoniazid is prescribed to subjects randomized into Group 4 in the daily dose of 600 mg of orally in the morning after meals.

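### As written, the efficacy population requires a known drug concentration, which excludes the whole isoniazid control group

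*Combined protocol and SAP*

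**What the plan says.** All references are to the synopsis of the combined protocol and SAP.

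- **Efficacy and PK population (Number of subjects).** Patients need at least one dose of study drug and must be among those "whose study drug concentrations are known will be processed in the final statistical analysis of efficacy and pharmacokinetics". This is the only efficacy population in the text available.
- **Safety population (same section).** "The data of subjects of ITT population will be processed in the final statistical analysis of safety". No concentration condition is attached, and the ITT population is not defined in the text available.
- **Concentration sampling (Design).** "Venous blood samples are taken from all subjects in Groups 1, 2, and 3 (PBTZ169 monotherapy) to measure PBTZ169 levels". No sampling in Group 4 and no isoniazid assay is described.
- **Meaning of study drug.** The Design text uses it for both products: "every patient received the study drug (PBTZ169 or isoniazid) as a monotherapy for 14 consecutive days". The product sections separate them, with "Study drug code: PBTZ169" in one and isoniazid in another under "Comparator, dose and administration, batch number".
- **Role of the control (Design).** The trial is a "randomized open-label study of efficacy (in terms of early bactericidal activity), safety, and pharmacokinetics of PBTZ169 in parallel groups with active control".
- **Efficacy outputs (Statistical methods; Efficacy analysis).** Efficacy descriptives, the CFU and PCR tables and the graph of mean CFU change are all planned by treatment group. EBA is to be given with a two-sided 95% confidence interval. Nothing there sets Group 4 aside.

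**The concern.** A concentration condition is natural for a PK set. Attached to efficacy, it makes membership depend on an assay result that one randomized arm was never scheduled to have. An analyst cannot apply the sentence and also produce four-group efficacy tables.

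What is at stake is the descriptive isoniazid EBA and its interval. Without them the PBTZ169 results have no concurrent reference in an open-label trial, and the active control has no efficacy output. The rule would also drop any PBTZ169 patient who has CFU data but no known concentration, so entry to the efficacy set would depend on an event after randomization.

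**Working it through.** **1. Planned numbers (Number of subjects).** 15 + 15 + 15 + 7 = 52, which reproduces the stated total. The sample size is described as empirical, so there is no power figure to check.

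**2. Scheduled concentration samples per patient (Design).**
- PBTZ169, first dose: 1 pre-dose + 13 post-dose = 14.
- PBTZ169, last dose: 1 pre-dose + 15 post-dose = 16.
- PBTZ169, total: 14 + 16 = 30.
- Isoniazid: 0.

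**3. The rule applied to Group 4 under each meaning of study drug.**

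| Meaning | At least one dose? | Concentration known? | Qualifies |
|---|---|---|---|
| PBTZ169 or isoniazid | yes | no, none planned | 0 of 7 |
| PBTZ169 only | no | no | 0 of 7 |

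The provision to keep venous samples for additional parameters does not help, because no samples are planned in Group 4.

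**4. Size of the efficacy set.**
- As written: at most 45 of 52 (45/52 = 86.5%). Excluded: 7/52 = 13.5%, all from one arm.
- With the condition limited to PK: at most 52 for efficacy and 45 for PK.

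**5. Precision of the lost estimate.** The plan gives no SD, so the 95% half-width is in SD units, t(0.975, n−1)/√n, assuming complete planned groups.
- n = 7: 2.447/√7 = 0.92 SD.
- n = 15: 2.145/√15 = 0.55 SD.

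**6. Formal tests (Efficacy analysis).** The Kruskal–Wallis test compares dose levels of the study drug, and the Jonckheere–Terpstra test looks for a trend with increasing dose. Neither uses Group 4, so losing that group changes neither test.

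**7. PBTZ169 patients lost to the rule.** The number cannot be derived. It is probably small, since 14 samples are scheduled around the first dose alone.

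**8. What a restored isoniazid EBA would represent.** The Group 4 description in Design says "subjects receive isoniazid tablets at a standard daily dose of 600 mg for 4 days as a monotherapy". Later Design text and Comparator treatment duration give 14 days. Days of each EBA window that fall after monotherapy:

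| Window | If 4 days | If 14 days |
|---|---|---|
| EBA 0–2 | 0 of 2 | 0 of 2 |
| EBA 0–7 | 7 − 4 = 3 of 7 (43%) | 0 of 7 |
| EBA 0–14 | 14 − 4 = 10 of 14 (71%) | 0 of 14 |

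Of the three named windows, only EBA 0–2 is monotherapy under every version. This discrepancy is separate from the population rule, but it decides how the day 7 and day 14 control values may be labelled.

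**The case against.** The strongest reply is that this is loose drafting. The sentence joins two conditions to two analyses, and the sponsor may have meant dosing for efficacy and concentrations for PK. The Efficacy analysis section supports that reading: it uses whatever measurements are available and states no concentration condition. That is, however, a rule for missing values and not a population definition, and the population sentence does not make the split. The intent is plausible, but the wording still needs correcting.

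Second, only synopsis-level text is available, and an undefined ITT population suggests that populations may be defined elsewhere. This stands as a caveat.

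Third, the conflict with the planned outputs is by implication. The stated goals concern PBTZ169, no test against isoniazid is planned, and the tables refer to treatment groups without saying four. That is fair, but in a trial that randomizes to four groups, with isoniazid named as active control, the ordinary reading includes Group 4.

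Fourth, the consequence is modest: one descriptive estimate from at most 7 patients, with no effect on error rates or power. This stands and limits the severity. The interval widths also assume full enrolment. The Pharmacokinetic and pharmacodynamic analysis section says the study was terminated early, so actual numbers are unknown.

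Finally, the text available states sputum collection from all subjects only at the first treatment visit (V1). Later collection in Group 4 is inferred from the by-group outputs.

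**Conclusion.** The concern holds: the sentence is wrong as written. Under either meaning of study drug, 0 of 7 planned isoniazid patients qualify for the efficacy analysis. That is 13.5% of the planned sample and the entire control arm. The result is loss of the descriptive control EBA and its interval. Loss of Group 4 has no effect on the dose-comparison tests, and the number of PBTZ169 patients affected is unknown and probably small.

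This should be fixed, but it does not threaten the primary dose comparison, and it can be recovered at reporting provided Group 4 sputum was collected as the by-group outputs imply. Confidence is medium. The conclusion rests on planned numbers and on no fuller population definition existing outside the text available.

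**What to change.** - Limit the known-concentration condition to the PK and PK/PD analyses (Groups 1 to 3).
- Define the efficacy population as all randomized patients in Groups 1 to 4 who took at least one dose of their assigned drug, PBTZ169 or isoniazid, using available CFU and PCR data. This keeps the plan's own dosing condition.
- If a fuller population definition exists elsewhere, align this sentence with it.
- If results were already produced under the present rule, report exclusions by group and add the isoniazid EBA with its 95% confidence interval.
- Reconcile the passages on the duration of Group 4 monotherapy before day 7 and day 14 isoniazid values are labelled as monotherapy EBA.

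The cost is the rewording of one population sentence and at most a rerun of the descriptive efficacy tables. No new data or patients are needed.
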